6.0 STUDY PROCEDURES

6.1 VT or PVC Ablation will be Performed According to Standard-of-Care Clinical Practice

Duration (mins)	STANDARD CLINICAL PROTOCOL	RESEARCH PROTOCOL	
		EP team	Anesthesia team
---	Pre-procedure holding room		Pre-drug muscle strength (grip and NIF)
60-140*	Clinical ablation procedure completed		
5	Post-ablation EPS & inducibility	Pre-drug EPS & inducibility	NIF, tidal volume, minute ventilation, ABG
5	Post-ablation ICE survey	LVERP & conduction time testing	
5	Post-ablation hemodynamics	Pre-drug hemodynamics	
3		Study drug given	
10		PK/PD blood sampling with measurement of ECG intervals and Fick cardiac output	NIF, tidal volume, minute ventilation, ABG
5		LV ERP & conduction time testing	
5		Post-drug hemodynamics	
2		Post-drug inducibility testing	
5			
---	Procedure completed		2-hour post-drug muscle strength (grip and NIF) and ABG
5	Post-procedure care unit		

Table 2. List of peri-procedural clinical and research activities. NIF: negative inspiratory force; ICE: intracardiac echocardiogram; LVERP: left ventricular effective refractory period; PK/PD: pharmacokinetics/pharmacodynamics.

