6.2 List of Encounters Detailing the Clinical and Research Activities

Encounter 1: Enrollment and Informed Consent

- Performed by the study team in the Vanderbilt Arrhythmia Clinic or Vanderbilt University Hospital.

Encounter 2: Time of Ablation

- The participant will arrive the morning of ablation to the EP pre-op holding room and undergo standard preparations for ablation according to the clinical protocols (e.g. labs, vitals, exam, procedural consent).
- The participant will undergo baseline muscle (grip) and respiratory (NIF) strength testing in the pre-op area.
- The participant is then transported to the operating room (EP lab) where standard of care ablation is performed under the direction of the clinical team. See section 6.1 for full details.
- Research activities will begin after completion of the ablation portion of the ablation procedure. Research activities occur concurrently with clinical activities and are performed by a dedicated physician and nurse team to avoid extending overall case time.
- The clinical post-ablation EP study with programmed ventricular stimulation will serve as the baseline (pre-dantrolene) assessment of cardiac electrophysiology parameters (conduction and refractoriness) and ventricular arrhythmia inducibility. Data analyses are performed offline following the case to avoid adding procedural time. See sections 6.3 to 6.6 for full details.
- Hemodynamic monitoring is routinely performed during ablation with an arterial line and pulmonary artery (PA) catheter (aka. Swann-Ganz Catheter). See sections 6.7 to 6.10 for full details. The pre-dantrolene arterial blood pressure mean right atrial, PA systolic, PA diastolic, mean PA pressure, and pulmonary artery wedge pressures will be recorded.
- Blood samples will also be drawn for calculation of a Fick cardiac output and for the pharmacokinetic (PK)/pharmacodynamic (PD) analysis. See section 6.12 for full details of the PK/PD analysis. A 2 mL sample from the femoral venous, arterial, and distal PA catheter will be collected.
- I.V. dantrolene will be administered over 3 minutes. Peak drug levels occur rapidly allowing the data collection protocol to proceed without delay.
- The post-dantrolene hemodynamics will be recorded.
- The post-dantrolene EP study with programmed ventricular stimulation will be repeated.

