- A 2 mL sample from the femoral venous, arterial, and distal PA catheter will be collected at 5, 10, 15, and 20 minutes post-dantrolene. The total amount of blood collected during the ablation is 30 mL.
- Respiratory mechanics (tidal volume, rate, minute ventilation) and an arterial blood gas (ABG) will be measured at 0, 10, and 20 minutes, and need for additional respiratory support will be assessed continuously as is standard care (see Section 6.13).
- The clinical and research activities will be complete, and the participant will leave the operating room awake, extubated, and hemodynamically stable.
- The participant will undergo baseline muscle (grip) and respiratory (NIF) strength testing in the post-op recovery area and an ABG will be measured 120 minutes after study drug was initiated

Encounter 3: Post-ablation Day 0-2.

- Following ablation, the participant will be returned to the EP holding room. It is clinical standard-of-care for patients to remain in the hospital at least overnight for monitoring. They will be under nursing observation and on continuous cardiac telemetry and oximetry. They will be on strict bedrest until post-operative Day #1 and they will be ambulated with assistance the morning after the procedure.
- 2 mL blood samples will be drawn at intervals of 4 to 12 hours for up to 48-hours during the post-ablation period. No more than 15 mL total will be drawn. We will use indwelling catheters whenever possible for blood collections. All patients will have indwelling catheters throughout the duration of study, and we do not anticipate needing to perform phlebotomy with a fresh stick during the study. See section 6.12 for full details.

- The research protocol is complete when the participant is discharged from the hospital.

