between the two study arms. For instance, if the pre-drug PA diastolic pressure measurements have a SD of 4 mmHg, we will have 80% power to detect a difference of +/- 2.4 mmHg in PA diastolic pressure. If the pre-drug average PA diastolic pressure is 12 mmHg, this means a 20% change in the treatment arm is detectable assuming there is no change in the control arm. Each primary endpoint will be tested at the two-sided 5% significance level.

Inducibility Endpoints: The primary hypothesis in Aim 3 tests whether RyR2 inhibition with dantrolene reduces the susceptibility to ventricular arrhythmias. Susceptibility to ventricular arrhythmias is measured by testing the inducibility of VT/VF using programmed ventricular stimulation.

Primary Analysis Aim 3:

Inducibility of Ventricular Arrhythmias: Ventricular arrhythmias are defined as monomorphic or polymorphic VT, or VF. The primary endpoint is either a sustained hemodynamically stable ventricular arrhythmia of ≥ 10 seconds duration or an unstable ventricular arrhythmia requiring termination (with pacing or defibrillation), or two episodes of non-sustained ventricular arrhythmia defined as an episode lasting 3-9 seconds. To maximize statistical power, the primary analysis utilizes an ordinal endpoint that measures the relative inducibility based on the stage of the induction protocol and the arrhythmia induced (**Table 5**). Multivariable regression models are built. Univariable logistic regression modeling will be used to test whether treatment with dantrolene is associated with the category of inducibility (ordinal endpoint) measured post-study drug with adjustment for the stage of inducibility measured pre-study drug. Multivariable modeling includes additional adjustment for age (continuous), sex, amiodarone exposure (yes/no), change in beta-agonist exposure, and time from start of drug to post-drug stimulation protocol. Models will be evaluated for goodness-of-fit, and internally validated for calibration/discrimination with bootstrap.

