Secondary Analyses Aim 3: A binary endpoint of inducibility (yes/no) is analyzed using logistic regression with the same covariate adjustment described for the primary analysis. Another secondary analysis tests the idea that RyR2 inhibition with dantrolene may alter inducible ventricular arrhythmias due to changes in conduction and refractoriness and hemodynamic improvement. An ordinal variable defining the cardiac rhythm stability class is analyzed (**Table 6**) using multivariable ordinal logistic regression. A secondary analysis will explore all the ventricular arrhythmia susceptibility endpoints for an interaction between cardiomyopathy type (ischemic versus non-ischemic) and treatment with dantrolene. Definitions: 1) Stable monomorphic VT is mean arterial pressure at 10 seconds (MAP_{10}) or immediately prior to termination of >50 mmHg; 2) Unstable VT is MAP_{10} or prior to termination of <50 mmHg; 3) Pleomorphic VT is more than one QRS morphology for 3 or more consecutive beats during the same VT episode; and 4) Polymorphic VT is a continually changing QRS morphology.⁵⁴

Sample Size and Power Aim 3: Primary Endpoint: The sample size selected for this trial was calculated to adequately power the analysis of the inducibility endpoint in Aim 3 which is an ordinal variable (Table 5). With $N=84$ patients (randomized to placebo and treatment in 1:2 ratio) with an expected 50% of patients in the placebo arm non-inducible, and 10% in each of the other categories, the study will achieve 80% power to detect an odds ratio (OR) of 0.3 at the two-sided significance level of 5%. With an anticipated 20% withdrawal rate prior to study drug, up to a total number of 105 patients will be enrolled in the study to ensure statistical power. Secondary Endpoints: 1) The binary status of inducibility (yes/no). With an effective sample size of 84, the study provides 80% power to detect an OR of 0.25, and a 70% power to detect an OR of 0.3 at the two-sided significance level of 5%.

Assessment of Safety (Aim 3): An interim analysis will be performed by the DSMB when 50% of the target enrollment is reached to test for an association between dantrolene or placebo and significant adverse events/harm. In order to preserve statistical power for the secondary analyses, the interim analysis will not include early stopping rules for efficacy. Although none of our Phase I pre-clinical or clinical data have raised

Table 5. Ordinal Inducibility Endpoint

	Category	

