Least inducible	0	No sustained VT/VF or NSVT
	1	1 episodes of NSVT with S4
↓	2	1 episodes of NSVT with S3
↓	3	1 episodes of NSVT with S2
↓	4	2 episodes of NSVT with S4*
↓	5	2 episodes of NSVT with S3*
↓	6	2 episodes of NSVT with S2*
↓	7	Sustained VT/VF with S4
Most inducible	8	Sustained VT/VF with S3
	9	Sustained VT/VF with S2

*the category assigned for 2 episodes of NSVT is based on the extrastimulus used to induce the second episode of NSVT.

Table 6. Secondary analysis of rhythm stability

	Category	
Least Stable	1	Ventricular Fibrillation
	2	Polymorphic VT
↓	3	Pleomorphic VT
↓	4	Unstable Monomorphic VT
Most Stable	5	Stable Monomorphic VT
	6	No Inducible VT/VF

safety concerns, and no adverse events have been observed, we planned the assessment of safety, which will be based on the frequency of adverse events. Other safety data such as blood pressure will be considered. All adverse events recorded during the study will be summarized. See Ethical Aspects of the Proposed Research for DSMB.

Respiratory Mechanics and Ventilation Endpoints: To monitor adequacy of ventilation, maintain safety, and measure the effect of dantrolene administration on ventilation, the anesthesiologist will monitor respiration and oxygenation as is standard of care for all patients during procedures and surgeries. The primary endpoint of the Respiratory Mechanics substudy is the incidence of the addition of respiratory support, including bag/mask ventilation, CPAP, BiPAP, LMA, or tracheal intubation, from the time of study drug administration until 120 minutes after study drug administration. Placement of airway support devices is at the discretion of the attending anesthesiologist and will be based on standard safety parameters such as oxygen saturation, adequacy of ventilation, and airway obstruction. Secondary endpoints include additional markers of respiratory mechanics and strength including negative inspiratory force, dynamometer measured grip strength, accelerometer (respiratory rate, tidal volume, minute ventilation), markers of gas exchange (arterial pH, pCO₂, pO₂, base excess), and electrolytes. Tidal volume, respiratory rate, and minute ventilation parameters will be continuously collected (recorded every minute) as available. We will summarize these data prior to study drug administration and at 10 and 20-minutes after dantrolene administration.

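### The all-cause airway-support endpoint runs through post-drug VT/VF induction, so support triggered by an induced arrhythmia could dilute a respiratory harm of dantrolene

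*Combined protocol and SAP*

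**What the plan says.** Section 10.0 (Respiratory Mechanics and Ventilation Endpoints) defines the substudy's primary endpoint as "the incidence of the addition of respiratory support, including bag/mask ventilation, CPAP, BiPAP, LMA, or tracheal intubation", counted "from the time of study drug administration until 120 minutes after study drug administration". On who decides, it says: "Placement of airway support devices is at the discretion of the attending anesthesiologist". The basis is standard safety parameters, with saturation, ventilation and obstruction as examples. Section 6.2 adds that "need for additional respiratory support will be assessed continuously as is standard care". No cause is attributed, nothing is split at induction, and support given during an arrhythmia is not shown separately.

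In Section 6.1, Table 2 lists "Post-drug inducibility testing" after study drug, PK/PD sampling, refractory-period and conduction testing, and hemodynamics. Section 6.2 agrees: "The post-dantrolene EP study with programmed ventricular stimulation will be repeated". The inducibility endpoint in Section 10.0 includes "an unstable ventricular arrhythmia requiring termination (with pacing or defibrillation"), and its primary hypothesis is that dantrolene lowers susceptibility to these arrhythmias. Section 6.1 describes most patients as under monitored anesthesia care with moderate to deep sedation.

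**The concern.** Two routes lead to the same count. One is weakness or sedation from dantrolene, which the substudy is meant to measure. The other is airway support given around an induced unstable rhythm or a shock. If the antiarrhythmic hypothesis is right, the second route is used more often on placebo, so its events offset those of the first. A finding of no excess support on dantrolene would then be hard to read as no respiratory effect. Section 2.0 says that this effect matters if the drug is to be repurposed.

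The plan allows for induced arrhythmia elsewhere: the hemodynamic model (Section 10.0, Primary Analysis, Aim 2) adjusts for it. The respiratory endpoint has no counterpart.

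**Working it through.** **Timing.** By Table 2, dosing takes 3 minutes, PK/PD 10, refractory-period and conduction testing 5, and hemodynamics 5. Induction therefore starts about 3 + 10 + 5 + 5 = 23 minutes after the start of dosing, well inside 120 minutes. The table's durations may be slightly misaligned, so take 20 to 25 minutes.

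**The plan's own figure.** No event rate, sample size or power is stated for the respiratory endpoint. The nearest stated figure is power for binary inducibility: 80% at an odds ratio of 0.25 and 70% at 0.3, with 84 patients randomised 2:1 and "expected 50% of patients in the placebo arm non-inducible". A two-sided 5% normal-approximation test with 28 and 56 patients gives 80.2% and 70.0%, so those inputs reproduce. At 0.3, dantrolene inducibility is 0.3/1.3 = 23.1%.

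**Inputs for the dilution.**
- Allocation 56 versus 28, and odds ratio 0.3 for induction (Section 10.0).
- Sustained arrhythmia on placebo, from the post-ablation series in Section 1.5: (38 + 9)/165 = 28.5%. On dantrolene, odds 47/118 × 0.3 = 0.1195, so 0.1195/1.1195 = 10.7%. Using this series for the trial is an assumption; its monomorphic VT lasted over 30 seconds, whereas the trial uses 10.
- VF only: 9/165 = 5.5% on placebo. On dantrolene, odds 9/156 × 0.3 = 0.0173, so 1.7%.
- Assumed: true support risk *r* of 5% on placebo and 30% on dantrolene, and a chance *q* that a triggering arrhythmia leads to support. Neither is in the documents.
- Test: two-sided Fisher's exact, one of the tests that the general strategy names for categorical data.

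**Formula.** With *i* the risk of a triggering arrhythmia, observed risk = 1 − (1 − *r*)(1 − *i* × *q*).

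Example, sustained VT/VF, *q* = 10%: placebo 1 − 0.95 × (1 − 0.0285) = 7.7%; dantrolene 1 − 0.70 × (1 − 0.0107) = 30.7%; difference 23.0 points.

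| *q* | Sustained VT/VF: difference | Power | VF only: difference | Power |
|---|---|---|---|---|
| 0 | 25.0 | 79% | 25.0 | 79% |
| 5% | 24.0 | 73% | 24.8 | 78% |
| 10% | 23.0 | 67% | 24.6 | 77% |
| 20% | 21.1 | 56% | 24.2 | 75% |
| 30% | 19.1 | 45% | 23.8 | 72% |

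**No true respiratory effect.** Ignoring overlap, the spurious difference in favour of dantrolene is (28.5 − 10.7) × *q* = 17.8 × *q* points: 0.9, 1.8, 3.6 and 5.3 points at *q* = 5%, 10%, 20% and 30%.

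**How much is due to imbalance.** If dantrolene left induction unchanged at 28.5%, the difference would be 25 × (1 − 0.285 × *q*): 24.6, 24.3, 23.6 and 22.9 points, with power 76%, 72%, 65% and 59%. Part of the power loss is therefore background events common to both arms; the rest comes from the imbalance.

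**Direction.** Ignoring overlap, the sign follows the difference in inducibility, so a rise on dantrolene inflates the apparent harm. With overlap at 30% versus 5%, inflation begins once dantrolene inducibility exceeds 0.95/0.70 = 1.36 times that of placebo.

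**The case against.** The strongest reply concerns size. No source supports any value of *q*, and several features point to a low one. Section 1.5 chose the 10-second definition partly to make cardioversion less likely. Section 9.0 withholds study drug from patients who are unstable or fail the hemodynamic criteria. Patients already on controlled ventilation have less scope for an addition of support. All of this stands.

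A reader might infer that every inducible patient is at risk of arrhythmia-triggered support. With 50% versus 23.1% in place of 28.5% versus 10.7%, power would fall to 60%, 42% and 28% at *q* = 10%, 20% and 30%. The documents do not support that. The inducibility endpoint includes pairs of 3-to-9-second runs, six of the nine inducible categories in Table 5 are non-sustained, and nothing suggests that brief self-limited runs lead to airway support.

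A reader might also infer that the endpoint is invalid, or that the conclusion should rest on counts that exclude arrhythmia-triggered support. Neither follows. All-cause support is a valid randomised comparison and matches the aim in Section 1.6. Excluding episodes by cause relies on a judgement about a post-randomisation event that treatment may change.

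Contamination is also not the main limit on inference: at 15% versus 5%, Fisher power is 17.5% with none at all. Ventilation and blood gases at 10 and 20 minutes come at or before induction and are largely unaffected, though they are secondary and only summarised.

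**Conclusion.** The point holds as one of dilution. The window contains deliberate induction of VT/VF, the endpoint does not attribute cause, and the direction follows from the trial's own hypothesis. It is conditional on dantrolene changing inducibility: the odds ratio of 0.3 is an effect the trial is sized to detect, not one that has been observed.

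The size is not known. Under the assumptions shown, a 25-point harm would appear as 19 to 24 points if sustained VT/VF is the trigger, and as about 24 to 25 if only VF is. Masking is a tempting word, but no scenario in the table hides the harm. What is weakened is the inference from no excess support to no respiratory effect. The remedy is cheap and is best put in place before data collection, since triggers and times are hard to reconstruct afterwards.

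**What to change.** Keep all-cause support over 120 minutes as the primary endpoint, and add the following:

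- Record the start time and trigger of every support episode, with the trigger assigned blind to treatment.
- Prespecify two supportive analyses by arm: (a) support started before post-drug stimulation begins, when the arms differ only by drug; and (b) full-window support with arrhythmia- or shock-triggered episodes shown separately.
- State that no excess support will be read as no respiratory effect only if these analyses agree with the primary count and with the ventilation, blood-gas and negative inspiratory force measures.

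Adjusting for post-drug induction in a model is not a substitute, because treatment may affect it.

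The cost is one or two case report form fields and a short addition to the analysis plan, with no change to clinical care. The pre-stimulation count covers only about 20 to 25 of the 120 minutes. It will have few events and will miss later weakness from a drug with a mean half-life of 10 hours (Section 6.12), so it can only support the primary count.

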Dropouts and replacement: To ensure adequate statistical power, we will account for up to a 20% rate of patient withdrawal from the study prior to randomization (for reasons such as non-study related procedural complications, hemodynamic instability, prolonged case duration), therefore up to 105 participants may need to be enrolled for 84 participants to complete the study.

Study Drugs: The investigational compound is dantrolene sodium (RYANODEX, Eagle Pharmaceuticals Inc, Woodcliff Lake, NJ). Ryanodex is supplied in a single dose vial by the manufacturer and it is reconstituted with 5 mL of sterile water prior to use. Each vial contains 250 mg of Ryanodex. Based on results from the pilot study, Ryanodex will be administered as an I.V. push over 3 minutes at a dose of 1 mg/kg. Ryanodex was tested in a Phase I study and safely tolerated in doses ranging from 1 mg/kg to 2.5 mg/kg. It is approved for use in adults with malignant hyperthermia at a recommended dose of 2.5 mg/kg. The calculated dose is based on measured body weight with a maximum dose of 250 mg used in our trial.

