6.12 Pharmacokinetic (PK)-Pharmacodynamic (PD) Analysis

PK/PD analysis will be performed by [name] (Lipscomb University). Ryanodex is a new formulation of dantrolene (nanoparticle suspension for injection) with enhanced aqueous solubility designed for rapid I.V. administration. The FDA determined that our proposal is exempted from requirements for an Investigational New Drug application (see accompanying letter from FDA). The PK of Ryanodex have been investigated in healthy volunteers at a dose range of 1 to 2.5 mg/kg and demonstrated a dose-proportional increase in dantrolene exposure with a peak concentration observed 1 minute after drug administration. Mean PK parameter estimates are independent of dose with a mean half-life of 10 hours, volume of distribution of 36.4 L, and systemic clearance of 2.5 L/hr. One major determinant of the short-term effects of many cardiac drugs is the concentration of drug within the myocardial tissue. Previous *in-vivo* studies evaluating the myocardial uptake of drugs in humans using a transcoronary blood sampling technique have demonstrated that lipophilic drugs like dantrolene exhibit rapid uptake into myocardial tissue with peak myocardial tissue content (1-4% of dose administered) being achieved within 0.5-5 minutes after I.V. bolus.^{56,57} To define the PK/PD relationship of dantrolene and its short-term effect on the specific hemodynamic (PA wedge pressure, Fick cardiac output) and EP parameters (electrocardiogram intervals [RR, PR, QRS, QT]), femoral venous, arterial, and PA distal blood samples will be collected simultaneously from indwelling sheaths in all subjects at the pre-dantrolene timepoint and at 5, 10, 15, and 20 minutes post-dantrolene. Arterial drug concentrations will be assumed to represent dantrolene concentrations present in the ascending aorta and reflect concentrations entering the coronary circulation. As such, the temporal relationship between dantrolene concentrations (arterial and venous) and peak hemodynamic and EP effects will be evaluated using PK/PD modeling approaches to determine direct response correlations or a potential time lag in response.

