6.13 Measurement of Respiratory Mechanics and Ventilation

To enhance the safety of the study protocol and enable research on the effect of dantrolene on respiratory mechanics, the study team will include cardiac anesthesiologists (Drs. [name], [name], [name], [name], and [name]) and will specifically study the effect of dantrolene on respiratory mechanics. Prior to the procedure, a baseline measurement of respiratory muscle strength will be obtained with a negative inspiratory force test (NIF), which is a quick, non-invasive bedside breathing test. During the procedure, to monitor adequacy of ventilation, maintain safety, and measure the effect of dantrolene administration on ventilation, the anesthesiologist will monitor respiration oxygenation as is standard care for all patients during procedures and surgeries. If the patient is already under general anesthesia with controlled ventilation (either with laryngeal mask airway [LMA] or endotracheal tube [ETT]), attempts will be made to have the patient spontaneously breathing with neuromuscular blockers reversed. These measurements include respiratory rate, minute ventilation, tidal volume, as well as arterial blood gas measurements (pH/pO₂/pCO₂/BE/Na/K/Cl/Ca). These measurements will be recorded prior to study drug administration and at 10 and 20 minutes after study drug administration. Finally, two hours and again at 24 hours after study drug administration, a NIF will be repeated to assess whether the respiratory muscle strength has returned to baseline. An arterial blood gas will also be repeated at 2 hours after study drug administration (sample obtained from the radial arterial line).

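### Ventilation is recorded every minute, but minutes 1-9 and 11-19 after study drug have no planned summary, so a brief fall that needs no added support would not be reported

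*Combined protocol and SAP*

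**What the plan says.** In the combined protocol and SAP, section 10.0 (Respiratory Mechanics and Ventilation Endpoints) sets the recording density: "Tidal volume, respiratory rate, and minute ventilation parameters will be continuously collected (recorded every minute) as available". Its next sentence sets the reporting: "We will summarize these data prior to study drug administration and at 10 and 20-minutes after dantrolene administration".

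Two procedural sections give the same times. Section 6.13 says "These measurements will be recorded prior to study drug administration and at 10 and 20 minutes after study drug administration". Section 6.2 says respiratory mechanics and the blood gas "will be measured at 0, 10, and 20 minutes, and need for additional respiratory support will be assessed continuously as is standard care".

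The substudy's primary endpoint is a different measure, the addition of respiratory support, counted "from the time of study drug administration until 120 minutes after study drug administration". Ventilation is one of several secondary markers, which section 1.6 says will be compared between groups. The General Statistical Strategies in section 10.0 assign repeated measurements to mixed-effect models, but do not mention ventilation.

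On timing, section 5.0 says "Ryanodex will be administered as an I.V. push over 3 minutes". Section 6.12 reports, for healthy volunteers, "a peak concentration observed 1 minute after drug administration" and a "mean half-life of 10 hours, volume of distribution of 36.4 L, and systemic clearance of 2.5 L/hr".

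**The concern.** The plan collects a minute-by-minute series and commits to reporting three points of it. No section names a minimum, an area, a block mean or a model for the values in between. The stated plasma peak falls in the first unsummarised stretch.

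Section 1.6 calls the drug's effect on respiratory mechanics unclear, and section 2.0 says defining it matters for any repurposing. A short, sub-clinical dip soon after the push is one form that effect could take, and the planned summary cannot show it. Other early signals are followed through time: ECG intervals every minute for 20 minutes (section 6.11) and arterial pressure every 2 minutes (section 6.9). If no summary of the intervening minutes is fixed now, any later look at them will be chosen after the data are seen.

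**Working it through.** **1. Coverage.** Per-minute recording over minutes 1-20 gives up to 20 post-drug values per patient. Named summaries use minutes 10 and 20. Unsummarised: 20 - 2 = 18, namely minutes 1-9 (9 values) and 11-19 (9 values). This assumes complete data, whereas the plan says as available. It also reads each summary as a single-minute value, which section 10.0 does not say outright.

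**2. The plan's pharmacokinetic figure.** Inputs from section 6.12: V = 36.4 L, CL = 2.5 L/h. Half-life = ln 2 × V / CL = 0.693 × 36.4 / 2.5 = 10.09 h. The stated 10 h reproduces within 1%.

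**3. Level at the summarised times.** With one compartment and a peak at 1 minute, relative level = exp(-ln 2 × (t - 1) / 600), t in minutes:

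- 5 min: 99.5%
- 10 min: 99.0%
- 20 min: 97.8%

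The documents give no distribution phase. Suppose a fraction f of the peak is lost with half-life h. Relative level = f × exp(-ln 2 × (t - 1) / h) + (1 - f) × exp(-ln 2 × (t - 1) / 600). For assumed f of 0.3-0.7 and h of 2-10 min, the level is 33-85% of peak at 10 minutes and 29-77% at 20 minutes. How much of the peak the summary misses therefore rests on an assumption from outside the documents.

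**4. Time zero.** The dose takes 3 minutes. If the peak is 1 minute after the end of the push, it falls at minute 1 on a clock started at the end, and at minute 3 + 1 = 4 on a clock started at the beginning. Either is inside minutes 1-9, but the 10-minute value moves by 3 minutes relative to the dose. Section 6.2 times the 2-hour blood gas from initiation of study drug, while sections 6.13 and 10.0 say only after administration.

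**5. Precision, under assumed autocorrelation.** For minute-to-minute correlation ρ and unit within-patient variance:

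- mean of minutes 10 and 20: (1 + ρ^10) / 2
- mean of all 20 minutes: (1/20) × [1 + 2 Σ (1 - k/20) ρ^k], k = 1 to 19

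| ρ (assumed) | two-point mean | 20-minute mean | within-patient reduction | fall in standard error if between-patient residual variance is also 1 (assumed) |
|---|---|---|---|---|
| 0.5 | 0.500 | 0.140 | 72% | 1 - √(1.140/1.500) = 13% |
| 0.8 | 0.554 | 0.351 | 37% | 1 - √(1.351/1.554) = 7% |
| 0.9 | 0.674 | 0.555 | 18% | 1 - √(1.555/1.674) = 4% |

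The two-point mean is a comparator used here; the plan does not propose it. The gain also presumes an effect that is roughly constant over 20 minutes. An effect confined to minutes 1-9 would be diluted to 9/20 = 45% in a 20-minute mean, so an overall mean is not the summary that would find a brief dip.

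**The case against.** The case for leaving the plan alone is substantial. The 10- and 20-minute points match the blood-gas schedule, so ventilation and gas exchange can be read together. Respiratory compromise that matters clinically is captured elsewhere: need for support is assessed continuously, added support is the substudy's primary endpoint from dosing onwards, and all adverse events are summarised. The general mixed-model rule could be applied to these data.

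Most of this stands, and it rules out three stronger readings that a reader might draw:

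- **That the intervening values are thrown away.** No section says so. They are recorded and kept, but no summary is named for them.
- **That the period of highest exposure is missed.** The stated half-life leaves levels near peak at 10 and 20 minutes unless a distribution phase is assumed. The 0.5-5 minute uptake figure in section 6.12 is for myocardium. The documents give no uptake time for respiratory muscle.
- **That precision suffers heavily.** The larger percentages concern within-patient error only, under assumed correlations. They shrink once between-patient variance is counted.

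What does not stand is that the gap is already closed. The support endpoint depends on the anesthesiologist's decision to intervene, so it does not see a fall that stops short of that. The general mixed-model rule is not tied to ventilation, and the specific sentence in section 10.0 names three times.

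**Conclusion.** The concern holds in a limited form. The plan names no summary for minutes 1-9 and 11-19, up to 18 of 20 post-drug values per patient. The result that could be lost is a fall in ventilation that recovers by minute 10 and leads to no added support. The documents do not say how likely such a fall is, and they do not establish that minutes 10 and 20 are poor choices on pharmacokinetic grounds. On the assumptions shown, the standard error might fall by about 4-13%, so precision is a modest secondary argument. This is a minor point about a secondary substudy endpoint. No sample size, power or alpha changes.

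**What to change.** Keep the pre-drug, 10- and 20-minute values, reported alongside the blood gases, and add to section 10.0:

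1. **Time course.** A between-arm comparison of all available minutes 1-20 in a mixed model with arm, 5-minute time block, arm by time block, and the mean of the pre-drug minutes as baseline, with patient as a random effect. State which pre-drug minutes count.
2. **Lowest value.** Each patient's lowest 3-minute average over minutes 1-20, compared by arm. This is the summary aimed at a brief dip.
3. **Time zero.** State whether the clock starts at the beginning or the end of the 3-minute push, and use the same choice in sections 6.2, 6.13 and 10.0.
4. **Which minutes count.** Limit both analyses to minutes of spontaneous breathing. Section 6.13 allows for patients under controlled ventilation and promises only attempts to restore spontaneous breathing, so report by arm how many patients and minutes are excluded.
5. **After support starts.** State how these minutes are handled, because the readings then reflect the support. One option is to give a patient the worst rank in the lowest-value summary once support begins and compare arms with the Wilcoxon rank sum test already named in section 10.0. Rescue then does not hide the largest falls.

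The cost is a short paragraph and a little analysis work; no new measurement is needed. The main limitation is completeness. Because data are recorded only as available, report the number of usable minutes by arm next to the results.
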